9.0 DURATION OF STUDY

The study includes hysterectomy with identification of sentinel lymph nodes on consecutive LREC and HREC patients.

The patient may withdraw from the protocol at any time prior to surgery or at any time until retrieval of postoperative data until 2 year after surgery.

The study was initiated at Lund university hospital (From january 2019) with potential later inclusion of a second or more investigating centers which will motivate a revision of the study protocol related estimated time for enrollment of patients and for accreditation of the second centre and surgeons. The annual volume of endometrial cancer patients in Lund is close to 200 with an estimated 85% suitable for minimally invasive surgery and inclusion in the study.

Related statistical analyses below a total of 362 patients will need to be included with an interim analysis after 150 patients.

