At any time during the conduct of the trial, if it is the opinion of the investigators that the risks (or benefits) to the patient warrant early closure of the study, this recommendation should be made in writing to the SMC. Alternatively, the SMC may initiate suspension or early closure of the study based on its review of the investigator reports.

Study Monitoring / study accrual oversight

The study principal investigator, any local principal investigator and study coordinator will conduct meetings (teleconferenced) every 6 months to discuss the protocol. The Study-PI and local-PI can call a meeting to convene at additional times if deemed necessary, for example following statistical review at the interim period if stopping the study for either achieved goals or futility. Apart from the monitoring described below, the number of node positive patients and potential false negative SLN's will be monitored continuously by e-mail to the study coordinator by the use of the study number assigned to each patient.

In case of identified inconsistencies or missing data, additional source documents (identified only by unique patient number) will be requested from the site to resolve ongoing inconsistencies.

The principal investigator and/or the study coordinator will, if deemed necessary by the principal or second participating center perform audits of informed consents and subject eligibility.

Data Management

Preoperative, intraoperative and postoperative data from each surgery will be recorded on the standardized study sheets. These study sheets will be made available to each study site. Each study site will be allocated a study number which will serve as the prefix to the case number. For example, Lund university Hospital will be allocated the prefix "Lu" and the first study patient will have the study number "LU-001. Each investigating center will hold a record with the full identification of patients whereas data otherwise should only identify the patient by the study number (see above).

Staff at the individual centers will be responsible for completing the data collection sheet for each patient and all data will continuously be entered into a common secured password

secured database using the designated study numbers. Upon interim analysis the full data will be monitored by the study coordinator, the principal investigator, local principal investigator and study statistician.

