Separate analysis of patient data from individual sites can only be performed with the written permission of the study principal investigator.

Early Study Closure

Death will be reported according to section 10.1 above and per local IRB reporting guidelines. The SMC will review all reported deaths monthly. Early closure of the study will be based on judgement of the SMC.

The study will be stopped for futility reasons as described under the statistics section.

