11. STATISTICAL CONSIDERATIONS

This study is designed to evaluate the ability of the sentinel node (SLN) technique to determine pelvic lymph node metastases in patients with low- and high risk endometrial cancer as a replacement for a full lymphadenectomy in the latter and as an increased diagnostic procedure in the former.

The main statistical endpoint will be to evaluate the SLN concept by a non-inferiority analysis, i.e its ability to detect nodal metastatic disease compared with an estimated proportion which with a 50/50% distribution of LREC and HREC result in approximately 12% of women having pelvic nodal metastases. This will be tested against 8% metastatic SLN's as null-hypothesis. With a one-sided analysis (Alfa-error of 5% and 80% power) 362 patients need to be included with a planned interim analysis after 150 patients.

If then 22 or more patients are identified as SLN-node positive the null-hypothesis will be rejected and the study closed. If 12 or fewer patients are identified as SLN node positive the study will be closed for futility. If the number of node positive patients is between 12 and 21 the study will continue to enroll a total of 362 patients (Fleming, 1982).

The measurements of leg volume/lymphedema are based on an estimated risk for lymphedema following SLN only of 1% (null hypothesis) compared with the group of SLN positive (HREC and LREC) with an estimated risk of 4% (20% node positive with 20% risk of lymphedema) with an estimated distribution between group of 88% SLN negative and 12% SLN positive with restaging (SLN+LND). A total of 169 patients need to be included with a planned interim analysis after 65 patients. If 3 or more patients in the SLN+LND group have lymphedema the null hypothesis can be rejected provided no more than one patient in the SLN only group have developed lymphedema.

BIBLIOGRAPHY

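### The interim rule gives 12 positives of 150 two opposite actions, and no final rejection count for 362 is stated; the design's 5% and 80% require stopping at 12 and rejecting at 38

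*Combined protocol and SAP*

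**What the plan says.** Section 11 (Statistical considerations) sets a one-sample test of a null rate of 8% SLN-positive patients against an expected 12%: "With a one-sided analysis (Alfa-error of 5% and 80% power) 362 patients need to be included". There is one interim analysis after 150 patients, with three instructions:

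- Efficacy: "If then 22 or more patients are identified as SLN-node positive the null-hypothesis will be rejected and the study closed".
- Futility: "If 12 or fewer patients are identified as SLN node positive the study will be closed for futility".
- Continuation: "If the number of node positive patients is between 12 and 21 the study will continue to enroll a total of 362 patients".

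The section cites Fleming (1982) for the design. It gives no number of positives among 362 that rejects the null at the final analysis.

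The other sections that touch on the rule add no counts. Section 9.0 repeats the totals: "a total of 362 patients will need to be included with an interim analysis after 150 patients". Section 10 mentions a meeting "following statistical review at the interim period if stopping the study for either achieved goals or futility", and under Early Study Closure it refers back to Section 11: "The study will be stopped for futility reasons as described under the statistics section".

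**The concern.** A single-arm test decided by a count needs exactly one action for each count, fixed before the data are seen. Two things are missing here.

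1. **The interim regions do not fit together.** If the continuation range includes its endpoints, 12 both closes the study and continues it. If it excludes them, 12 is settled but 21 has no stated action, because early rejection starts at 22. Neither reading gives every count one instruction.
2. **The final decision rule is not printed.** It can be derived from the plan's inputs, but only after the first point is settled and the method is fixed. Different reasonable choices give 38 or 39.

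The count in question is not remote. Twelve of 150 is exactly 8%, the most likely interim result under the null, and it decides between closing the study and enrolling 362 − 150 = 212 more patients. Section 10 also says that "the number of node positive patients and potential false negative SLN's will be monitored continuously by e-mail to the study coordinator", so an unclear rule would be interpreted by people who have followed the count as it grew.

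**Working it through.** **Inputs (Section 11; 150 and 362 also in Section 9.0).** p0 = 0.08, p1 = 0.12, one-sided alpha 5%, power 80%, n1 = 150, N = 362, early rejection at 22 or more. Let a be the highest interim count that stops for futility (12 or 11, depending on the reading) and r the final rejection count.

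**Assumptions.** All 150 and all 362 patients are analysed, and futility is binding. The plan does not use the word binding, but it says that the study will be closed or stopped.

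**Formula.** With X1 ~ Bin(150, p) and X2 ~ Bin(212, p):

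P(reject) = P(X1 ≥ 22) + Σ over x = a+1 to 21 of P(X1 = x) · P(X2 ≥ r − x)

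**Step 1: reproduce the plan's 362.** Keep the interim bounds fixed. For each total from 160 to 419, take the smallest r with alpha at most 5% and ask whether power reaches 80%.

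- 12 stops (a = 12): the first total that qualifies is **362, with r = 38**. At 361 with r = 38, alpha is 4.82% and power 79.75%, just short. The next total that qualifies is 371 (r = 39).
- 12 continues (a = 11): the first total is 359 (r = 38: 4.74%, 80.45%), then 360, then 367. The total 362 does not qualify.

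The plan's own sample size therefore points to stopping at 12.

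**Step 2: final cut-offs at 362.**

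| r | 12 stops: alpha | 12 stops: power | 12 continues: alpha | 12 continues: power |
|---|---|---|---|---|
| 37 | 6.82% | 83.38% | 7.22% | 85.28% |
| 38 | **4.97%** | **80.15%** | 5.21% | 81.77% |
| 39 | 3.55% | 76.27% | 3.69% | 77.62% |

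Only the pair 12 and 38 meets both limits. With 12 stopping, P(X1 ≥ 22) is 0.42% at 8% and 18.74% at 12%. For r = 38 the rest, 4.97 − 0.42 = 4.55% and 80.15 − 18.74 = 61.41%, comes from the final look, so most of the power depends on the number that is not printed.

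**Step 3: what an analyst might use instead.** A single-look exact test at 362 gives P(38 or more | 8%) = 5.33% and P(39 or more | 8%) = 3.65%, so it would choose 39. Within the two-stage design with 12 stopping, moving from 38 to 39 changes the verdict in 4.97 − 3.55 = 1.42% of trials at 8% and in 80.15 − 76.27 ≈ 3.9% at 12%.

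**Step 4: how often the final rule is needed (12 stopping).**

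| True rate | Futility | Early rejection | Continue to 362 |
|---|---|---|---|
| 8% | 57.6% | 0.4% | 42.0% |
| 12% | 7.8% | 18.7% | 73.4% |

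**Step 5: trials that sit at 12.** P(X1 = 12) is 11.92% at 8% and 3.35% at 12%. If such a trial continues, it needs 38 − 12 = 26 or more of the next 212, which has probability 1.98% at 8% and 48.42% at 12%. The joint probability of sitting at 12 and later rejecting is 0.1192 × 0.0198 = 0.24% at 8% and 0.0335 × 0.4842 = 1.62% at 12%. Expected enrolment at 8% is 150 + 212 × 0.420 ≈ 239 if 12 stops. If 12 continues it is 150 + 212 × (0.420 + 0.119) ≈ 264.

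**Step 6: the exclusive reading.** P(X1 = 21) is 0.44% at 8% and 7.13% at 12%. If 21 were treated as early rejection, r = 38 would give alpha 5.18% and power 80.32%.

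**The case against.** **The overlap is a wording slip.** The futility sentence is explicit, the continuation range is loosely phrased, and 362 follows only if 12 stops. Under the exclusive reading, 21 meets neither stopping rule, so continuing is the natural default. The overall effect is also small: alpha moves from 4.97% to 5.21%, and the joint probabilities in Step 5 are 0.24% and 1.62%. All of this is fair, and it shows how to repair the text. It does not remove two opposite instructions at the most likely null count, and it does not supply the final cut-off.

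**Binding futility is inferred.** Section 10 leaves early closure to the judgement of the safety committee. If futility were not binding, 38 would give alpha 5.45%, and 39 would give 3.82% with power 78.8%. However, the sentence on committee judgement follows text about deaths, while the futility sentence refers to Section 11 and is mandatory. Binding is the better reading, but the plan should say so.

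**There is no slack at 362.** Sections 6.0 and 8.0 take patients converted to open surgery before SLN removal out of the accuracy evaluations, so fewer than 362 may be analysed. With 355 analysed and cut-off 38, alpha is 4.02% and power 77.2%. With the interim look at 152, alpha is 5.06%. This stands: a clause that recomputes the cut-off protects alpha but not power.

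**The value 38 is inferred.** Fleming's normal-approximation bounds at 362 also give a final count of 38, but interim bounds of 9 and 21, not 12 and 22. The original design calculation therefore has to be checked before 38 is printed.

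**Conclusion.** The concern holds, and the text must be corrected. As written, one interim count lacks a single instruction under either reading of the range, and the rejection rule for the main endpoint is absent at the final look. The sample size is not in error: 362 is reproduced exactly with stopping at 12, early rejection at 22 and final rejection at 38 (alpha 4.97%, power 80.15%).

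The size is modest for the overlap and larger for the missing count. A trial lands on 12 with probability 11.9% at a true rate of 8% and 3.4% at 12%, and the two readings can then end in opposite conclusions. Using 39 in place of 38 lowers power from 80.1% to 76.3%, below the stated 80%. These figures rest on exact binomial calculation, binding futility, and all 150 and 362 patients being analysed.

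**What to change.** In Section 11, change the lower end of the continuation range so that it reads 13 to 21. After the study statistician has confirmed the count, and that futility is binding, against the original design calculation, add:

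> At the final analysis the null hypothesis is rejected if 38 or more of 362 patients are SLN-positive (exact two-stage one-sided alpha 4.97%, power 80.1%, futility rule binding). If the numbers analysed at the interim or final look differ from 150 or 362, the final cut-off is recomputed by the same exact two-stage method, as the smallest count with alpha at most 5%.

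Keep 362 as the number of patients included. If fewer are analysed, report the power for the analysed number, since the recomputed cut-off controls alpha only.

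The cost is one corrected number, two added sentences and a check by the study statistician. Sample size, enrolment and conduct do not change.

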5.0 TREATMENT PLAN/ FOLLOW UP

Patients with metastatic SLN's shall be planned for a restaging procedure including pelvic and paraaortic lymph nodes.

Importantly, all intraoperative adverse events associated with the study intervention and the study drug (ICG) will be recorded in protocol as the separate time used for the detection and removal on SLN's. Likewise, complications associated with the restaging procedure shall be included on an intention to treat basis.(additional CRF)

All adverse events, including postoperative until 30 days, shall be evaluated whether attributable to the study intervention or not.

Measurement of leg volume as an objective parameter of lymphedema shall be performed at one and two year follow up and at symptoms.

Symptoms associated with lymphedema shall be evaluated by a designated QoL Form used before surgery, after surgery at symptoms, and at one and two years after surgery. A symptoms score shall be used at every follow up.

NOTE: Surgeons' skill and adherence to protocol will be verified as described above.

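### The lymphedema comparison is sized at 169 women, but its only decision rule is a pair of fixed counts with no sample size attached; Section 11 should define the analysis set and use an exact two-group test at the end

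*Combined protocol and SAP*

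**What the plan says.** The lymphedema paragraph of Section 11 gives these design inputs:

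- Reference risk: "estimated risk for lymphedema following SLN only of 1% (null hypothesis".
- Comparison risk, for SLN-positive women: "estimated risk of 4% (20% node positive with 20% risk of lymphedema".
- Split: "estimated distribution between group of 88% SLN negative and 12% SLN positive with restaging (SLN+LND".
- Size: "A total of 169 patients need to be included with a planned interim analysis after 65 patients".
- Rule: "If 3 or more patients in the SLN+LND group have lymphedema the null hypothesis can be rejected", on condition that at most one SLN-only woman has developed lymphedema.

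The rule follows directly after the interim at 65 and names no sample size. Nothing further is printed for a final analysis.

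Section 5.0 (Treatment plan/follow up) sets the measurement: "Measurement of leg volume as an objective parameter of lymphedema shall be performed at one and two year follow up and at symptoms". The table in Section 7.0 adds a preoperative measurement. Neither names a subset or a cap. Section 3 leaves only women with previous lower limb lymphedema out of this part of the study.

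For the whole study, Section 9.0 says "a total of 362 patients will need to be included with an interim analysis after 150 patients". Under Section 11 the study closes at 150 with 22 or more, or 12 or fewer, SLN-positive women.

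**The concern.** The plan does not say which women form the lymphedema test set, which sample size the limits 3 and 1 belong to, or what happens if enrolment passes 169 or ends at 150. An analyst could choose between 169 and 362 after seeing the data.

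Absolute limits also behave badly when the sample size is not fixed. The limit of one SLN-only case becomes harder to meet as more women are measured, even when the SLN-only risk is exactly the assumed 1%. Lymphedema is the only harm outcome with a formal test in Section 11. At stake is whether a real excess after restaging could be declared, using measurements that are already scheduled.

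**Working it through.** **1. Reproducing 169.** Take a one-sample two-stage design with p0 = 1%, p1 = 4% and 65 women at stage 1. One-sided 5% and 80% power are printed for the primary endpoint only and are assumed to carry over. Stop for futility at 0 cases, reject at 3 or more of 65, and reject at the end at 5 or more of 169. The bounds 0 and 5 are inferred, not printed.

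P(reject) = P(X1 ≥ 3) + Σ over x = 1, 2 of P(X1 = x)·P(X2 ≥ 5 − x), with X1 ~ Bin(65, p) and X2 ~ Bin(104, p).

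- At p = 1%: 0.0443. At p = 4%: 0.8003. With 168 women the power is 0.7975, so 169 is the smallest total with these bounds.
- P(3 or more of 65 | 1%) = 0.028. As a one-sample limit at 169, 3 would carry a type I error of 0.240.

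So the printed 3 fits 65, not 169. The calculation also treats the women as one sample, whereas the rule compares two groups.

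**2. Group sizes at 12% SLN+LND.** 0.12 × 65 = 7.8, 0.12 × 150 = 18, 0.12 × 169 = 20.3 and 0.12 × 362 = 43.4. Rounded, SLN+LND against SLN only is 8/57, 18/132, 20/149 and 43/319.

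**3. The limit of one SLN-only case.** For m SLN-only women at 1%, P(at most 1) = 0.99^m + m × 0.01 × 0.99^(m−1).

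- m = 57: 0.564 + 0.325 = 0.889
- m = 149: 0.224 + 0.337 = 0.560
- m = 319: 0.041 + 0.131 = 0.171 (expected cases 319 × 0.01 = 3.2)

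**4. The whole rule.** Multiply by P(3 or more) in SLN+LND, taking the groups as independent binomials. The 20% is the risk printed in the bracket of the comparison risk, read here as the risk after restaging.

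| N | P(SLN only ≤ 1) | P(SLN+LND ≥ 3 at 20%) | Rule rejects at 20% |
|---|---|---|---|
| 65 | 0.889 | 0.203 | 0.18 |
| 169 | 0.560 | 0.794 | 0.44 |
| 362 | 0.171 | 0.995 | 0.17 |

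At 4% after SLN+LND the rule rejects with probability 0.025 at 169 and 0.042 at 362.

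**5. An exact two-group test on the same data.** One-sided Fisher test at 5%, SLN-only risk 1%. Power is the sum of the joint binomial probabilities over all tables with p ≤ 0.05.

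| SLN+LND risk | N = 169 | N = 362 |
|---|---|---|
| 4% (printed) | 0.13 | 0.26 |
| 10% (assumed; not in the documents) | 0.48 | 0.80 |
| 20% (printed in the bracket) | 0.87 | 0.99 |

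Precision also improves. The exact 95% interval for the SLN+LND risk is 5.7–43.7% with 4 of 20 and 10.0–36.0% with 9 of 43.

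**6. How far the cohort can differ from 169.** The largest excess is 362 − 169 = 193, less the women with previous lymphedema, whose number is not given. Closure at 150 leaves a shortfall of 169 − 150 = 19. From the primary limits, the chance of 13 to 21 positives among 150 is 0.73 at a true 12%, so continuing to 362 is the more likely outcome under the plan's own assumption.

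**The case against.** The strongest reply is that the 3/1 counts are interim limits. They follow the mention of 65, the primary paragraph likewise gives its interim limits straight after naming its interim, and step 1 agrees. At 65 the SLN-only condition is met with probability 0.89. On this view, 0.44 and 0.17 apply the limits where the plan never prints them. That stands as the likely reading, and a reader should not infer that the plan fixes 3 and 1 as its limits for 169. But the counts then reject with probability only 0.18 at 65, and no final rule exists at all.

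A reader might also infer that women beyond 169 are unused. The documents do not support this. Section 1 makes leg volume up to two years an estimation objective with no cap, and a secondary test needing fewer women than the primary is ordinary. These women are missing only from the stated test.

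Nor does the rule weaken with more data at every risk: at 4% its rejection probability rises slightly, though it stays below 5%. And enlarging the sample does not repair the one-sample sizing, since power at 4% is only 0.26 even at 362.

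Finally, the count rule is stricter than a 5% test: with 1% risk in both groups it rejects with probability 0.0006 at 169 and 0.0016 at 362. Part of the power gap reflects that. The plan states no wish for so strict a level.

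**Conclusion.** The point holds as a gap in specification with a measurable cost. Section 11 defines neither the lymphedema analysis set nor a final rule, and the one rule it prints cannot be carried to other sample sizes. At 1% against 20% with an 88/12 split, that rule rejects with probability 0.18, 0.44 and 0.17 at 65, 169 and 362 women, against 0.87 and 0.99 for the exact test at 169 and 362.

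These figures assume independent groups, complete measurement and the printed 1%, 20% and 12%. That the 3 belongs to the interim is an inference. The 48% to 80% gain depends on an assumed 10% risk. Neither the plan nor the proposed test gives 80% power for the two-group comparison at 4%.

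**What to change.** In the lymphedema paragraph of Section 11:

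1. State that the final analysis includes every eligible woman with a preoperative and a one-year leg volume, whatever number is enrolled (150 to 362). Call 169 a planning figure, neither a cap nor a minimum; closure at 150 would make a minimum of 169 unattainable.
2. For the final analysis, replace the absolute limits by a one-sided exact two-group test with an exact confidence interval for the risk difference, and print the significance level for this comparison.
3. State that the 3/1 counts, if kept, apply only to the interim at 65.
4. Do not claim 80% power for the two-group comparison at 4%; give the power in step 5 of the working instead.

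The cost is SAP wording, because the measurements are already scheduled. The drawback is a later result if enrolment reaches 362. Section 9.0 implies about 0.85 × 200 = 170 women a year, so 193 more take 193/170 ≈ 1.1 years. Those women are to be followed for two years in any case.

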Attribution: Attribution is the determination of whether an adverse event is related to a medical treatment or procedure. The categories of attribution are:

Definite: The adverse event is clearly related to the study drug

Probable: The adverse event is likely related to the study drug.

Possible: The adverse event may be related to the study drug.

Unlikely: The adverse event is doubtfully related to the study drug.

Unrelated: The adverse event is clearly NOT related to the study drug.

Unexpected Adverse Event: An unexpected adverse event is an event not mentioned in the package insert/ manufacturer's instructions or the specificity or severity of which is not consistent with the package insert/ manufacturer's instructions.

The grading described beneath and the attribution described above will be used for categorization of unexpected adverse events.

